Educational attainment		✓											✓
Current educational status					✓		✓			✓		✓	✓
Employment during pregnancy				✓									
Current employment status					✓		✓			✓		✓	✓
Age of child when mother began school or work c					[✓]		[✓]			[✓]		[✓]	[✓]
Continuation/discontinuation of WIC participation				✓	✓	✓	✓	✓	✓	✓	✓	✓	✓
Location of WIC service receipt				✓	✓	✓	✓	✓	✓	✓	✓	✓	✓
If WIC discontinued, age of child when WIC discontinued				✓	✓	✓	✓	✓	✓	✓	✓	✓	✓
If WIC discontinued, reasons for leaving WIC				✓	✓	✓	✓	✓	✓	✓	✓	✓	✓

a Questions will be asked at the first interview (could be prenatal, 1 month, or 3 month)

b Asked at enrollment if enrolled in study after child's birth; asked at 1 month if enrolled in study prenatally. The bracketed checks indicate times when this could be asked conditional upon time of enrollment.

c Asked the first time postnatally that the mother reports that she is currently working for pay. The bracketed checks indicate times when this could be asked.

- Some variables are asked only once during the study, but the timing is conditional upon participant characteristics such as questions asked at either enrollment/screening or 1 month depending on whether the mother is a prenatal or postnatal enrollee (i.e., due date, infant DOB, single or multiple birth, child name, child sex, child ethnicity, child race); the age of the child when the mother returned to work, asked the first time postnatally the mother reports currently working for pay; or questions about timing and reasons for leaving WIC, asked when the mother indicates she no longer receives WIC.
- Other variables will be asked periodically over the course of the 24 months to capture changes over time (i.e., marital status, new pregnancy, household size, household

income, presence of infant's father, receipt of public assistance, household food insecurity, educational attainment, educational status, and employment status).

- Only a small number of variables will be asked at every post-birth interview, as current status is required for each interview (i.e., respondent still the child's caregiver; continuation/discontinuation of WIC receipt; location of WIC service receipt)

The complete list of domains and variables can be found in the Database Plan (Deliverable 10b) delivered on September 7, 2012.

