Figure: Percentage of all WIC mothers still breast-feeding, by age of the infant and whether the mother reports knowing about the special WIC food package for breastfeeding women who do not accept infant formula for WIC (Months 1-13)	IFPS-1 p166	Both
Table: Frequency of top 10 reasons women stop breastfeeding within the first 2 and 6 weeks (Cumulative; Months 1, 3)	New	Both
Table: Frequency of top 5 reasons women stop breastfeeding within the first 6 weeks by infant health status and household demographics (Cumulative; Months 1, 3)	New	Both
Table: Frequency of top 5 reasons women stop breastfeeding by the magnitude of the difference between intended and actual breastfeeding duration	New	Both
Table: Percentage distribution of reasons for stopping breastfeeding between 2-3and 4-6 months (Months 3, 5,7)	New	Both
Table: Average Edinburgh Postpartum Depression Scale score by breastfeeding status (Month 3 )	New	Both
Table: Characteristics and circumstances of mothers breastfeeding (Months 1, 7)	New	Both
Table: (Model) Relative risks estimated by the multivariate models of rates of breastfeeding cessation (survival analysis) (Months 1-13)	IFPS-1 p168p168	Both
Figure: Percentage of WIC mothers still breastfeeding by age of the infant and reported receipt of none, one, two, or three WIC program components that support breastfeeding (Months 1-13)	IFPS-1 p173	Both

Table 7-2. Summary of analyses to be conducted (continued)

Table/Figure (Interview months)	Source	Sample
Initiation of Supplemental Foods: The Transitional Phase of Infant Feeding		
Table: Infant feeding patterns of WIC participants (by milk/food category) (Months 3-11)	FITSd S74	Both
Figure: Percentage of WIC mothers who have not yet initiated cereals, fruits, vegetables, and meats at each age of the infant (Months 1-13)	IFPS-1 p186	Both
Figure: Percentage of WIC mothers who have not yet initiated dairy foods, high-protein foods other than meats, and sweet/snack foods, at each age of the infant (Months 1-13)	IFPS-1 p188	Both
Table: Median age of the infant (in weeks) when specific supplemental foods are initiated by selected socio-demographic characteristics of the mother (Cumulative; Months 1-13)	IFPS-1 p189	Both
Table: Percentage of infants and toddlers consuming different types of milk and other beverages by age (Months 3-24)	FITS S40	Both
Table: Percentage distribution of combination feedings by age (Months 1-13)	New	Both

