**Model Specifications**

Several of the specific analyses shown in Table 7-2 involve estimating models. Table 7-3 provides the detailed specifications for these models. The first four models – the breastfeeding decision model, the formula supplementation model, the breastfeeding cessation model, and introduction of other foods model -- mirror models used in the previous IFPS-1 study. Initially, we will estimate these models primarily using the covariates that were used in the IFPS-1 study. This will facilitate the comparisons to the past research. We will also explore extending this work by making some improvements in the measurement of variables, the estimation method, and the covariates used. For these models, the additional covariates and estimation methods we propose to explore are noted in italics on Table 7-3. For many of the explanatory variables there are alternative proxy variables that we could use to measure the concept we are trying to capture. We will explore these alternative proxies if the initial variable proves to be insignificant. The weight and growth models shown in Table 7-3 are new.

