Formula Supplementation	
 
■ Time until formula supplementation
 
	
 
■ Survival analysis
 
	
 
■ Socio-demographics: Age, race/ethnicity, born in US, infant first born, use of childcare, education, worked during pregnancy
 
■ Maternal and infant health: Mother's post-delivery health status, infants health status, birth weight, reported problems breastfeeding
 
■ Prenatal attitudes, beliefs and knowledge: Perceived benefits of breastfeeding, perceived barriers, how long intend to breastfeed
 
■ Prenatal experience and advice: Receipt of advice to breastfeed from physician, receipt of breastfeeding information from non-WIC sources
 
■ WIC program experience: Education, peer counseling, breast pumps, time in WIC
 

Breastfeeding cessation	
 
■ Time until cessation
 
	
 
■ Survival analysis
 
	
 
■ Socio-demographics: Age, race/ethnicity, born in US, infant first born, education, use of child care
 
■ Maternal health: Reported breastfeeding problems
 
■ Breastfeeding practices: Current use of formula
 
■ Prenatal attitudes, beliefs and knowledge: Perceived benefits of breastfeeding, perceived barriers, how long intend to breastfeed
 
■ Prenatal experience and advice: Receipt of advice to breastfeed from physician, receipt of breastfeeding information from non-WIC sources
 
■ WIC program experience: Education, peer counseling, breast pumps, time in WIC
 
■ Return to work/school: Returned to work/school within 2 months
 

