Introduction of other foods	
 
■ Time until cereal
 
■ Time until fruits
 
■ Time until vegetables
 
■ Time until meats
 
	
 
■ Survival analysis
 
	
 
■ Socio-demographics: Age, race/ethnicity, born in US, household size, income, poverty level, use of child care, returned to work or school, education
 
■ Feeding practices: current use of formula
 
■ Attitudes, beliefs and knowledge: Belief formula provided from WIC is insufficient, parental assessment of baby's weight
 
■ Prenatal experience and advice: Receipt of breastfeeding information from non-WIC sources
 

Table 7-3. Proposed model specifications (continued)

Model	Dependent variable	Estimation methods	Minimum covariates to explore
			
 
■ WIC program experience: Education, time in WIC
 
■ Return to work/school: Returned to work/school within 2 months
 

Weight	
 
■ Child's weight/length (6, 12, and 24 months)
 
	
 
■ OLS
 
■ Quantile regression
 
	
 
■ Socio-demographics: Gender, race/ethnicity, income, born in US
 
■ Maternal/family health: Maternal BMI, paternal obesity, maternal diabetes, smoking during pregnancy, household food security (24 months only), maternal fruit and vegetable dietary intake (24 months only)
 
■ WIC program experience: Education, food package, time in WIC (and peer counseling for 6 month weight/length)
 
■ Child's health and physical activity: birth weight, premature, rapid early weight gain, physical activity indoors, physical outdoors (for 24 month measure) current sleep duration
 
■ Basic dietary intake: Breastfeeding duration, current intake of sweetened beverages
 
■ Feeding practices: Clean plate policy, track eating, careful not to feed too much
 

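### Used as worded, the exploratory 2-month return-to-work/school indicator in the cessation and other-foods survival models would count some mothers as exposed before they returned; the plan does not say how it enters.

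*Combined protocol and SAP*

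**What the plan says.** Table 7-3 gives the model specifications. For breastfeeding cessation the outcome is "Time until cessation" and the method is "Survival analysis". Table 7-2 reports this model over months 1 to 13, alongside figures by infant age, so time runs from birth. The covariate "Returned to work/school within 2 months" is listed for this model and again for introduction of other foods (cereal, fruits, vegetables, meats). It is not listed for formula supplementation. The foods row also carries an undated item, "returned to work or school, education".

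The 2-month item is in italics, and the text before Table 7-3 explains that "the additional covariates and estimation methods we propose to explore are noted in italics on Table 7-3". It is therefore an exploratory addition to the covariates carried over from the previous study.

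Neither Table 7-3 nor the rest of Chapter 7 says whether the item enters as fixed or time-varying, from a landmark, or only when the return came before the event. The same cessation row has an item worded as a current state: "Breastfeeding practices: Current use of formula".

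Table 3-2 in section 3.1 collects "Age of child when mother began school or work". Its footnote ties the question to the first postnatal report of working for pay.

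**The concern.** The indicator describes something that may happen at any time in the first 2 months of follow-up. Take a mother who stops breastfeeding at week 3 and goes back to work at week 7. A yes/no variable attached from birth puts her in the exposed group at her event, although the return came four weeks later and cannot have acted on it as an exposure already in place.

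Two errors follow. Time before the return is credited to the returned group, which dilutes a real effect. If weaning makes an earlier return easier, returns that follow weaning also appear to precede it, and an association arises where return has no effect.

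Early weaning is expected: Table 7-2 plans a tabulation of reasons for stopping within 2 and 6 weeks. Section 2.2 names employment among the influences on later feeding decisions, and section 7.3 places these models under causal analyses. The coefficient is likely to be read as an effect of returning.

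In the foods models this misclassification touches only foods introduced before the return, within the first 2 months. Cessation is the main concern.

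**Working it through.** The plan states no hazard ratio, event count or rate for these models, so there is no figure to reproduce. The check is a large simulation on assumed inputs.

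**Assumptions, none from the documents except the follow-up.** 40% weaned and 30% returned by 2 months before any effect of return; constant hazards; follow-up to 13 months (Table 7-2); 400,000 mothers per scenario; a one-covariate Cox model.

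- Weaning hazard: h = −ln(0.60)/2 = 0.255 per month.
- Return hazard: λ = −ln(0.70)/2 = 0.178 per month.

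**Step 1: how many exposed mothers weaned first.** With return unrelated to weaning, the share of those returning within 2 months who had already weaned is 1 − [λ/(λ+h)] × (1 − 0.60×0.70)/0.30 = 1 − 0.411 × 0.58/0.30 = 0.205, about 20%. In the simulation this rises to 32% and 38% when return is 2 and 3 times faster after weaning.

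**Step 2: estimated HR under three codings.** Fixed means yes/no from birth. Time-varying switches on at return. Landmark starts at 2 months among women still breastfeeding.

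| True HR | Situation | Fixed | Time-varying | Landmark |
|---|---|---|---|---|
| 1.0 | Return unrelated to weaning | 1.00 | 1.00 | 1.00 |
| 1.5 | No returns after 2 months | 1.37 | 1.50 | 1.50 |
| 1.5 | Returns continue after 2 months | 1.27 | 1.50 | 1.31 |
| 2.0 | No returns after 2 months | 1.69 | 2.0 | 2.0 |
| 2.0 | Returns continue after 2 months | 1.54 | 2.0 | 1.63 |
| 1.0 | Return 2 times faster after weaning | 1.21 | 1.00 | 1.00 |
| 1.0 | Return 3 times faster after weaning | 1.39 | 1.00 | 1.00 |

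Repeat runs differ by about 0.01.

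**Step 3: split the dilution.** For a true 1.5, the drop to 1.37 comes from mothers who weaned before returning. The further drop to 1.27 comes from mothers who return after 2 months and stay coded unexposed. The second part is a matter of definition (early return versus any return), and a 2-month landmark does not remove it.

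**Step 4: vary the rates.** With no later returns, return times uniform over 2 months, 15% or 30% returning, and 10%, 30% or 50% (w) weaned by 2 months:

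- Share weaned before return, 1 − w/(−ln(1−w)): 5%, 16%, 28%.
- True 1.5 under fixed coding: 1.44–1.45, 1.38–1.40, 1.31–1.33.
- True 2.0 under fixed coding: 1.87–1.88, 1.74–1.75, 1.58–1.61.

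With a true 1.0, constant return hazards and return 1.5 to 3 times faster after weaning, fixed coding gives 1.06–1.21, 1.08–1.32 and 1.11–1.45 for the same three values of w. Both problems grow with early weaning.

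**The case against.** The strongest reply is that the plan never says the covariate is fixed. It names a variable and a class of methods and leaves the coding of every covariate open. That is correct, and a reader who infers that the sponsor has chosen a fixed covariate goes beyond the text. What stands is that Table 7-3 is the specification an analyst will follow. The item is a once-only yes/no at 2 months, in contrast to the current-state wording used for formula in the same row. The remark in section 2.1 about timing and lagged influences, and the reference to past decisions in section 7.3, are not carried into this covariate.

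A reader might also infer that all the time-to-event models are affected, or that this is classical immortal-time bias. Neither follows. The item is absent from the formula supplementation model, and a mother need not still be breastfeeding to be classed as returned.

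A further objection concerns the question being asked. A mother who plans an early return may wean beforehand because of it. If such plans raise the weaning hazard 1.5-fold from birth (an assumption), fixed coding gives 1.50 and time-varying coding 1.29. This stands as a limit on interpretation. It does not rescue the indicator as worded, which cannot separate anticipation from a return made easier by weaning.

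Finally, the covariate is exploratory and no designated primary result depends on it. That limits the stakes but does not change what the coefficient estimates.

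**Conclusion.** The point holds in conditional form. Table 7-3 specifies, for cessation and for introduction of other foods, an indicator determined after time zero, with no rule to keep exposure ahead of the event. If used as worded, its coefficient is unbiased when return has no effect and does not depend on weaning, is pulled towards the null when return raises the hazard, and is spuriously above 1 when weaning hastens return.

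On the assumed 40% and 30% rates, the size is enough to change a reading, either by shrinking a real effect or by creating one. It rests wholly on those rates, which the documents do not supply; at 10% weaned by 2 months the dilution is slight. The cessation figures should not be carried over to the foods models, where events before the return may be few. The effect is on this coefficient and on adjustment for it. It is worth correcting before analysis because a better coding draws on an item already planned for collection.

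**What to change.** In Table 7-3, for the cessation and other-foods models, state that return to work/school enters as a time-varying covariate that switches on at the recorded child age at return (Table 3-2). Say whether the undated return item in the foods row is the same variable.

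If the early-return indicator is kept, use it only in a model that starts at 2 months among women still at risk. Label it as early versus later or no return, because it does not recover the effect of any return.

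The costs are small:

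- SAP wording and a counting-process data set.
- Reliance on recalled age at return. Table 3-2 first allows the question at 3 months, and Table 4-1 gives prenatally enrolled supplemental mothers no 3-month interview, so their first report comes at 7 months.
- Confirmation that the age item also dates return to school, since its footnote mentions paid work only. If it does not, the school part needs its own date or must be dropped from the covariate.
- A sentence in the interpretation that weaning in anticipation of a planned return is not captured.

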Table: Percentage of children (at 24 months) in each weight/length quintile by timing of the introduction of different types of solid foods (Cumulative; Months 1-13 & clinical records 24)	New	Both
Table: Child's weight/length quintile at 24 months by mothers average sweetened beverage and fruit and vegetable intake score (Month 24)	New	Both
Table: Percentage of children in top 20% and bottom 20% of the weight/length distribution at 12 and 24 months by breastfeeding experience and socio-demographics (Months 1, 3 and clinical records 12, 24)	New	Both
Table: Percentage of children in top 20% and bottom 20% of the weight/length distribution at 12 and 24 months by child's health, physical activity behavior, and rearing/feeding practices (Cumulative, Months 1-24 and clinical records 12, 24)	New	Both
Table: Average child weight/length gain in first 6 months by breastfeeding experience and gender (Months 1, 3 and clinical records 1, 6)	New	Both
Table: Average child weight/length gain in first 6-12 months by breastfeeding experience and gender (Months 1, 3 and clinical records 6, 12)	New	Both
Table: (Model) OLS regression estimates of the impact of the impact of socio-demographics and feeding practices on weight/length at 24 month (Cumulative; Months 1-24 and clinical records for 6, 12 24)	New	Both
Table: (Model) Quantile regression estimates of the impact of socio-demographics and feeding practices on weight/length at 6 month (Cumulative; Months 1-6 and clinical records for 6)	New	Both
Table: (Model) Quantile regression estimates of the impact of socio-demographics and feeding practices on weight/length at 12 month (Cumulative; Months 1-13 and clinical records for 6, 12)	New	Both
Table: (Model) Quantile regression estimates of the impact of socio-demographics and feeding practices on weight/length at 24 month (Cumulative; Months 1-24 and clinical records for 6, 12 24)	New	Both

Table 7-2. Summary of analyses to be conducted (continued)

Table/Figure (Interview months)	Source	Sample
Child’s Weight and Feeding Practices (continued)		
Table: (Model) Growth model estimates of the impact of socio- demographics and maternal health on weight gain trajectory of the child from birth to 2 years (Cumulative; Months 1-24 and clinical records for 0, 6, 12 24)	New	Both

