**Table 7-3. Proposed model specifications**

Model	Dependent variable	Estimation methods	Minimum covariates to explore
Breastfeeding decision	
 
■ Initiating breastfeeding
 
■ Breastfeeding at hospital discharge
 
 Measured dichotomously and categorically (all breastfeeding, combination, all formula)	
 
■ Logistic regression (dichotomous)
 
■ Multinomial logistic regression (categorical)
 
	
 
■ Socio-demographics: Age, race/ethnicity, born in US, father in house, infant first born, income, poverty level, education, worked during pregnancy
 
■ Maternal and infant health: Mother's post-delivery health status, infants health status (measured as in NICU or more than 6 weeks premature or very low birth weight)
 
■ Prenatal attitudes, beliefs and knowledge: Perceived benefits of breastfeeding, perceived barriers, breastfeeding intentions
 
■ Prenatal experience and advice: breastfed previous children, receipt of advice to breastfeed from physician, receipt of advice to breastfeed from family, receipt of breastfeeding information from non-WIC sources
 
■ WIC program experience: Education, peer counseling, time in WIC
 
■ Hospital experience: Mom's length of stay, baby's length of stay, receipt of formula or bottle in gift package, had baby friendly practices
 

Table 7-3. Proposed model specifications (continued)

Model	Dependent variable	Estimation methods	Minimum covariates to explore

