Growth	
 
■ Repeated measures of child's weight/length
 
	
 
■ Growth model
 
	
 
■ Socio-demographics: Gender, race/ethnicity, income Maternal/family health: Maternal BMI, paternal obesity, maternal diabetes, smoking during pregnancy
 
■ WIC program experience: Education, food package, time in WIC
 
■ Child's health and physical activity: Birth weight, premature
 
■ Basic dietary intake: Breastfeeding duration
 

We will estimate several variants of the breastfeeding decision model. First, we will use two alternatives for the dependent variable: initiating breastfeeding and breastfeeding at hospital discharge. Similarly, we will explore using dichotomous measures (yes, no) for these variables as well using categorical measures that capture mixing breastfeeding and formula feeding from the start. Additionally, we will have mother's prenatal attitudes collected prior to delivery (rather than retrospectively) and can also explore how their breastfeeding intentions for initiation and duration affect actual initiation and exclusivity. Finally, for this model we will explore the viability of using a summary index to capture the mother's attitudes, beliefs, and knowledge on breastfeeding and her hospital experience in place of the individual covariates in these groups.

Our estimates of the formula supplementation model and time until the introduction of other foods models will closely parallel the past work with few extensions. In estimating the formula supplementation model we will explore how breastfeeding intentions regarding duration (which is typically not collected) affect the time until formula supplementation. The covariates we will examine for predicting the time until breastfeeding cessation and the introduction of cereals, fruits, and vegetables will parallel those used in the IFPS-1 study.

For the new weight model, we will run separate models estimating weight/length for the children at 6, 12, and 24 months. In addition to including direct measures of toddler feeding practices (such as family has a clean plate policy), we will explore the viability of using summary measures of a range of toddler feeding practices to predict weight outcomes.

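### Table 7-3 does not confine rapid early weight gain to the 12- and 24-month weight/length models, and its Weight row lists no age at measurement

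*Combined protocol and SAP*

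**What the plan says.** **Models.** Section 7.5 says "we will run separate models estimating weight/length for the children at 6, 12, and 24 months". Table 7-3 has a single Weight row for all three, with OLS and quantile regression as methods, under the column heading "Minimum covariates to explore".

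**Covariates.** The child-health group reads "birth weight, premature, rapid early weight gain, physical activity indoors, physical outdoors (for 24 month measure) current sleep duration". Other items in the row carry their own age limit: "household food security (24 months only), maternal fruit and vegetable dietary intake (24 months only", and "time in WIC (and peer counseling for 6 month weight/length". Breastfeeding duration is also listed. Child's age at measurement is not.

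**Weights collected.** Section 4.10 has WIC-record measurements taken at 6, 12 and 24 months and requested at 7, 13 and 24 (also Table 3-3), with birth values from hospital records. Section 4.11 has home measurements at 7, 13 and 24 months for core-sample infants who left WIC and do not see a provider. Section 4.9 has provider records requested at 7, 13 and 24 months for core-sample infants who left WIC.

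**Data named for the outputs.** Table 7-2 lists "Quantile regression estimates of the impact of socio-demographics and feeding practices on weight/length at 6 month (Cumulative; Months 1-6 and clinical records for 6". The 12-month quantile model adds the 12-month record, and the 24-month model uses the 6-, 12- and 24-month records. The gain table is "Average child weight/length gain in first 6 months by breastfeeding experience and gender (Months 1, 3 and clinical records 1, 6". Its counterpart under research question 59 in Table B-1 names clinical records for months 1 and 5.

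**The concern.** The 6-month model is a named output for research question 59, on how feeding practices relate to growth. If the Weight row is applied as written at 6 months, the gain term ends at the weight that forms the outcome, and birth weight, where the gain starts, is in the same model. The coefficients of interest (breastfeeding duration, education, food package, time in WIC) would then be estimated after conditioning on part of the outcome.

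The second matter is age. The home-measured children are measured a month later than the WIC-record children at the two earlier ages. They are all WIC leavers, so measurement age is tied to time in WIC, which section 7.2 builds partly from days of current participation.

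**Working it through.** The plan gives no figure on this point to reproduce. All numerical inputs below are assumptions, except the 20 percent in step 5.

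**1. Can the gain term avoid the outcome at 6 months?** Scheduled weights up to that outcome are birth and the 6/7-month measure. Section 7.2 defines the plan's own early-gain measure as 0-6 months. Provider records could hold earlier dated weights, but only for core-sample children who left WIC. The 1- and 5-month clinical records named for the gain table appear in no collection section. On the schedule shown, the term therefore ends at the outcome weight. In the 12- and 24-month models a 0-6 month gain precedes the outcome and the problem does not arise.

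**2. Continuous gain.** 6-month weight = birth weight + (0-6 month gain). With both terms in the model, weight is fitted exactly. An OLS simulation shows this (n = 200,000; birth-weight SD 0.5 kg; 6-month weight SD 0.9 kg; birth to 6-month correlation 0.2-0.5; weight-length correlation 0.5-0.7; exposure effect -0.2 kg). R-squared for weight becomes 1.00 and the exposure coefficient 0. For the weight/length ratio, R-squared is 0.92-0.93 and the coefficient is again about 0.

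**3. Yes/no flag, feeding acting on weight only.**
- In the same simulation, with the top quarter of gain flagged, the ratio (x100) coefficient falls from -0.261 to -0.135 in one setting and from -0.240 to -0.113 in another. The losses are 1 - 0.135/0.261 = 48% and 1 - 0.113/0.240 = 53%.
- A second set-up has birth weight N(3.3, 0.5) kg and feeding 0/1 at 50%. Gain = 4.4 + d x 0.8 x feeding - 0.15 x (birth weight - 3.3) + 0.8 x noise, with d = 0.2 or 0.3. Length is N(66, 2.4) cm, with correlation 0.3, 0.5 or 0.7 with the gain noise and 0.3 with birth weight. The flag marks the top 20%, 25% or 33% of gain, which makes 18 settings. Loss = 1 - (coefficient with flag / coefficient without).

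| Method | Weight/length ratio | Weight-for-length residual |
|---|---|---|
| Quantile, 20th percentile | 35-53% | 18-50% |
| Quantile, 50th percentile | 37-54% | 19-54% |
| Quantile, 80th percentile | 43-61% | 21-60% |
| OLS | 35-53% | 19-52% |

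Example (d = 0.3, correlation 0.5, top 25%, ratio, median): 0.310 falls to 0.171, a loss of about 45%.

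**4. Yes/no flag, feeding also raising length.** In the second set-up by OLS (d = 0.3, top 25%), an assumed 0.3-0.5 SD effect on length changes the picture. The residual coefficient can change sign (0.107 to -0.009) or move away from zero (-0.059 to -0.144). The ratio loss runs from 61% to over 100%.

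**5. Age at measurement.** Assume 0.2-0.6 kg is gained between 6 and 7 months, on an assumed 0-6 month gain of 4.4 kg. For one child measured at 7 months, gain is overstated by 0.2/4.4 = 4.5% to 0.6/4.4 = 13.6%. Section 4.9 estimates that 20 percent of enrollees may leave WIC over the three years. If all of them were home-measured at 7 months, the error in the overall mean would be 0.20 x 4.5% = 0.9% to 0.20 x 13.6% = 2.7%. This is an upper bound: home measurement at this age also requires core-sample membership, exit by about 7 months and no provider visits.

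**The case against.** The strongest reply is that the plan never says the term enters the 6-month model. Table 7-2 gives that model only the 6-month record, while the 12- and 24-month models also have an earlier one. The list is a minimum to explore. It also contains other items that do not fit every age: section 7.5 describes "direct measures of toddler feeding practices (such as family has a clean plate policy", which is untagged in Table 7-3. A missing tag is therefore weak evidence of intent. This stands, and a reader should not infer that the plan prescribes a circular 6-month model. It does not settle the matter, because Table 7-2's record lists are incomplete: none names the birth record, although birth weight is a covariate.

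The 24-month tag after the activity items might be read back over the whole group. That would also remove birth weight and prematurity from the 6- and 12-month models, which is unlikely.

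The Database Plan, which section 2.1 cites for the full variable list and which was not available here, may define the term. If a 1-month weight did exist, a birth-to-1-month gain would avoid the outcome, but Table 3-3 and section 4.10 schedule none. Section 7.5 presents Table 7-3 as the place for detailed model specifications, so age-specific use belongs there.

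On age, an open list allows it to be added, and section 7.2 names weight-for-length, which relates weight to length rather than to age. Both points lower the stakes. Table 7-3 does not say whether its weight/length outcome is a ratio or a standardized score.

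**Conclusion.** The point holds as a gap in the specification. Table 7-3 does not exclude rapid early weight gain at 6 months, and using it there on the scheduled weights would distort the feeding and WIC coefficients. A reader might infer that those coefficients always shrink toward zero. That does not follow: roughly 20-60% is lost under a yes/no flag with an effect on weight only, but the sign can change when length is affected too. The certain result is the algebraic one, that continuous gain plus birth weight reproduces 6-month weight.

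The age omission is real but small overall, at most about 0.9-2.7% of mean 0-6 month gain on assumed inputs. The 4.5-13.6% figure is one child's gain error. It is neither a group bias nor the error in a model coefficient, for which the documents allow no figure. The age gap still falls only on WIC leavers, so it overlaps with time in WIC, and a comparison of leavers with stayers is not diluted in the way the overall mean is. The stated ages agree at 24 months.

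The change is worth making because it costs almost nothing. Confidence is medium, since intent at 6 months is unclear and the variable's definition was not seen.

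**What to change.** 1. State in Table 7-3 that rapid early weight gain is used only in the 12- and 24-month models, built from the birth and 6-month records, and give its cut-off if it is a flag.
2. Add exact age at measurement (measurement date minus birth date) to the Weight models, or use an age- and sex-standardized outcome.
3. Compute the 0-6 and 6-12 month gain tables per month of actual interval.
4. Reconcile the record months for the 0-6 month gain table (1 and 6 in Table 7-2; 1 and 5 in Table B-1) with sections 4.9 to 4.11 and Table 3-3.

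The cost is text changes to Tables 7-2, 7-3 and B-1 and a few derived variables. Birth date and sex (Table 3-2) and measurement dates (section 3.4, Table 3-3) are already collected.
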